4.2. Sample Size Estimation for Cost Effectiveness Analysis

We will perform an exploratory cost analysis using the cost data collected during this study. Based on the sample size estimation outlined in Willan et al², and cost and QALY estimations from past studies³⁻⁶, we estimated a range of sample sizes that will be required for a formal CEA. The lowest and highest observed change in QALY in the literature was 5-20%; similarly observed change in cost was 10-25%. Based on these the sample size requirement in the most optimistic case was 96 patients (48 in each group) and in the most conservative case was 740 patients (370 in each group) for a power of 80% and p-value if 0.05. Approximately 50% of the patients for whom the MSU is dispatched, and who meet inclusion criteria for enrollment into the study, will receive tPA. Hence, the total number of patients used for the CEA will have to be between 192 and 1480 patients. Even though the current study probably will not meet the

sample size requirement for the conservative case, it will help establish the expected cost and QALY changes for the MSU intervention (which have never been estimated before).

5. ANALYSIS PLAN

5.1. Phase III Trial Analysis

5.1.1. Treatment Group Comparability at Baseline

Although the random enrollment of participants to the two treatment arms and blinded review of tPA eligibility should ensure comparability with respect to known and unknown variables, imbalance may occur by chance. Descriptive statistics for baseline characteristics known or suspected to be associated with outcomes will be prepared for the two treatment groups for all randomized as well as all deemed “eligible for tPA” based on the blinded review. Chi-square statistics and Wilcoxon rank sum tests will be used to evaluate baseline differences between the arms for categorical and continuous variables, respectively. Any variables with baseline differences will be included in secondary adjusted analyses. Also, completers will be compared to non-completers (loss to follow-up for 90 mRS) on these baseline variables to indicate whether missingness may be considered random.

5.1.2. Primary Clinical Analysis

The mean uw-mRS at 90d along with corresponding two-sided 95% confidence intervals will be compared between groups using a two-sample t-test or Wilcoxon rank sum test if the assumption of normality does not hold. Although the mRS is an ordinal outcome, the difference between the uw-mRS categories has clinical significance and the t-test assumption and central limit theorem are likely satisfied. The primary analysis of uw-mRS will be adjusted for baseline uw-mRS, site, any baseline covariates that are different between the two groups, and covariates associated with mRS, including baseline NIHSS, age, pre-morbid mRS, and previous TIA/stroke, in a linear regression model. If the assumptions of the model are not satisfied, a restricted cubic spline will be used to model baseline continuous variables (NIHSS and age). If the linear regression with splines does not fit well, we will use ordinal logistic regression to adjust for the variables. If the proportional odds assumption fails, we will use logistic regression with mRS 0-1 vs 2-6 as the primary analysis. Assuming that the primary analysis doesn't use the following models, sensitivity analyses of the primary outcome will be conducted including ordinal (shift) analysis using a proportional odds model and proportion achieving a dichotomized outcome of mRS 0-1 vs 2-6 using binary logistic regression.

In response to peer review, we added post-hoc propensity score analyses using propensity scores as an alternative way to reduce any effects of confounding to estimate the effect of MSU group on dichotomized mRS (0-1 versus 2-6). The individual propensities for enrolling into the MSU versus EMS groups were estimated using a separate selection multivariable logistic regression model with variables site, baseline NIHSS, pre-stroke

mRS, age, Black race, gender, and dichotomized time from LSN to EMS/MSU arrival (>1hr versus ≤1hr). Standardized mean differences were used to assess covariate balance before and after weighting (all standardized mean differences were < 0.1). The predicted probabilities were used to calculate stabilized inverse probability weights (IPW). The 90-day uw-mRS was further described using means and standard deviations and by fitting a univariate linear regression with outcome (90-day uw-mRS), covariate MSU group, and IPW according to the propensity score. IPW analyses of all enrolled patients was added post-hoc to assess the chances of post-enrollment selection bias and to align analysis with overall MSU vs EMS management with outcomes discharge mRS and 24hr NIHSS.

Utility weights

The sample size was originally designed using the Dawn trial utility weights that were derived based on a United Kingdom sample and using the 3-level version of EQ5D. EQ5D-5L has been in use for more than a decade. However, the corresponding population-level utility weights for 5L had not been developed for many countries, and most countries only have population-level weights for the much older EQ5D-3L. In 2019 a study was published by Pickard et al. conducted a survey to develop utilities based on a US population and using the 5-level version of EQ5D (EQ5D-5L), which is more relevant to the participants in the BEST-MSU study. Using their Probit model estimated parameters to calculate utilities, in June 2020 we fit a linear regression model with these utilities (using 90-day EQ5D-5L) as the outcome and the 90-day mRS indicator variables as the independent variables to estimate our specific utility-weighted mRS. We also applied both the Dawn and the newly derived utility weights to the B-PROUD data and observed that results were consistent in the comparison of their mobile stroke unit data and their non-mobile stroke unit groups between these two weight choices. These were presented during the June 2020 study monitoring committee and were approved to use as the primary outcome of our trial. The weights based on the June 2020 data are presented in Table.

Table. Comparison of utility weights.

mRS	Dawn weights (previous MSU weights)	ENCHANTED trial weights	New proposed MSU
0	1	0.977	1
1	0.91	0.885	0.91
2	0.76	0.748	0.72
3	0.65	0.576	0.65
4	0.33	0.194	0.18
5	0	-0.174	0.05
6	0	0	0

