2.2. Study Outcomes

2.2.1. Primary Outcomes

- The utility-weighted modified Rankin Scale (mRS) at 90 days, comparing patients found eligible for tPA (based on a blinded review of the patient's chart, regardless of whether they were treated or not) on MSU weeks compared to patients on SM weeks.

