2.2.2. Secondary Outcomes

- Comparing patients found eligible for tPA (based on a blinded review of the patient's chart, regardless of whether they were treated or not) on MSU weeks compared to patients on SM weeks.
 - ordinal (shift) analysis of mRS at 90 days, and
 - proportion of patients achieving 90-day mRS 0,1 vs 2-6
 - 30% improvement from baseline to 24hr NIHSS
- The agreement between the VN on board the MSU with a VN remotely assessing a suspected stroke patient for treatment with tPA via TM in the MSU, and the rate of technical failures in conducting the TM consultation. N.B. Patients will include all enrolled patients on MSU weeks considered for tPA treatment.
- An exploratory cost-effectiveness analysis (CEA) of MSU versus SM using the Incremental Cost Effectiveness Ratio and Incremental Net Benefit estimate will be performed. N.B. The exploratory CEA will include all enrolled patients on MSU and SM weeks found eligible for tPA (based on a blinded review of the patient's chart, regardless of whether they were treated or not)

- Comparing all patients treated with tPA (whether or not adjudicated as tPA eligible) on MSU weeks compared to patients on SM weeks.
 - Utility-weighted modified Rankin Scale (mRS) at 90 days
 - ordinal (shift) analysis of mRS at 90 days, and
 - proportion of patients achieving 90-day mRS 0,1 vs 2-6
 - 30% improvement from baseline to 24hr NIHSS
- Comparing enrolled patients treated with tPA within 60 minutes of LSN onset according to published guidelines on either MSU or SM weeks, compared to similar patients treated 61-270 minutes after onset, adjusting for any imbalances in stroke severity (baseline NIHSS) between the groups at the time of treatment. N.B. Patients will include only those patients actually treated with tPA based on the final determination of the time LSN, and will include only patients meeting all inclusion and exclusion criteria.
 - utility-weighted mRS at 90 days,
 - ordinal (shift) analysis of mRS at 90 days
 - proportion of patients achieving 90-day mRS 0,1 vs 2-6
 - 30% improvement from baseline to 24hr NIHSS
 - Instead of dichotomizing into two groups based on time from LSN to tPA, logistic regression of 90-day mRS 0,1 vs 2-6, using a restricted cubic spline for time from onset to treatment, with visualization of spline term compared with the odds ratio

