the anticipated difference between groups if the MSU produces a substantial reduction in time to treatment, and felt that a difference of 0.07 is a more realistic goal. [name] did not participate in that decision since he is unblinded.

Assuming a 3:2 (1.5) imbalance, 5% LTFU, and using the pooled standard deviation of STEMO & No STEMO group ($sd=0.385$), numbers of patients needed to detect a difference of 0.07 using a 2-sample t-test is $N=1038$. Our LTFU so far has been around 5% so we expect this assumption to be reasonable. PCORI has agreed to the increase in sample size and sites sufficient to detect a 0.07 difference.

[figure not shown]

Figure. Reanalysis of a substantial number of completed stroke trials where conventional mRS outcomes were translated to uw-mRS. Effect sizes reported. From Broderick, et al.

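### SAP 5.1.2 fixes the order of its fallback models but not their triggers, so the primary estimand can change from a uw-mRS mean difference to an odds ratio without an auditable rule.

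*SAP*

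**What the plan says.** SAP 2.2.1 names one primary outcome: "The utility-weighted modified Rankin Scale (mRS) at 90 days, comparing patients found eligible for tPA", MSU against SM weeks. SAP 2.2.2 lists "proportion of patients achieving 90-day mRS 0,1 vs 2-6" among the secondary outcomes.

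SAP 5.1.2 makes an adjusted linear regression primary: "The primary analysis of uw-mRS will be adjusted for baseline uw-mRS, site, any baseline covariates that are different between the two groups", plus baseline NIHSS, age, pre-morbid mRS and previous TIA or stroke. Three fallbacks follow in order.

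1. If the linear model's assumptions are not met, NIHSS and age enter as restricted cubic splines.
2. "If the linear regression with splines does not fit well, we will use ordinal logistic regression to adjust for the variables".
3. "If the proportional odds assumption fails, we will use logistic regression with mRS 0-1 vs 2-6 as the primary analysis".

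The same section says of uw-mRS that "the t-test assumption and central limit theorem are likely satisfied".

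Protocol 7.B has no such chain. There the ordinal and mRS 0-1 models are sensitivity analyses of the primary outcome. The SAP's version log dates the alternative modelling to June 2020.

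**The concern.** Step 1 is model tuning: the treatment effect remains a difference in mean uw-mRS. Steps 2 and 3 change the quantity being estimated to a common odds ratio and then to an odds ratio for mRS 0-1. The null hypothesis of the primary test would then depend on a model check that the plan does not write down. No assumption is named for step 1 and no fit criterion for step 2. Step 3 names proportional odds but gives no test or level, and does not say whether the check covers the arm term or every covariate.

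Fit and proportional odds for the outcome model can be judged only once 90-day outcomes are in hand, yet nothing says who judges them or whether that person is blinded to arm. The SAP does take this care elsewhere. On the sample-size change, SAP 4.1 records that one team member "did not participate in that decision since he is unblinded".

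The end of the chain also works against the reason for the endpoint. Protocol 6.A.1 argues for uw-mRS because patients with pre-stroke mRS above 2 cannot achieve mRS 0 or 1. If so, any benefit to them is invisible under the fallback.

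**Working it through.** **1. The plan's own figure.** Inputs from SAP 4.1: difference 0.07, SD 0.385, ratio 1.5, 5% loss. Power 80% and alpha 0.05 are stated there for the earlier N of 693 and are assumed to carry over; two-sided is taken from the confidence interval in 5.1.2.

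SM patients = (1 + 1/1.5) × [0.385 × (1.960 + 0.842)/0.07]² = 395.7, so the evaluable total = 2.5 × 395.7 = 989.3. With loss: 989.3 × 1.05 = 1038.75, or 989.3/0.95 = 1041. The stated 1038 is reproduced.

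In reverse, 1038 × 0.95 = 986 evaluable, or 394 SM and 592 MSU. SE = 0.385 × √(1/394 + 1/592) = 0.0250; 0.07/0.0250 = 2.80; power = Φ(2.80 − 1.96) = 79.9%. The sample size therefore belongs to the mean difference alone.

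**2. Power of the mRS 0-1 fallback.** The documents give no SM rate for mRS 0-1, so 30-55% is assumed. The only stated effect on this scale is the 10 points in the futility rule (SAP 6.3). Unadjusted, two-sided 0.05:

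power = Φ[(d − 1.96·SE₀)/SE₁], with SE₀ = √[p̄(1−p̄)(1/394 + 1/592)] and SE₁ = √[p_SM(1−p_SM)/394 + p_MSU(1−p_MSU)/592].

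Example, 40% against 47%: p̄ = 0.442, SE₀ = 0.0323, SE₁ = 0.0321; (0.07 − 0.0633)/0.0321 = 0.21; power 58%.

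| SM rate | 7 points | 10 points | Difference for 80% power |
|---|---|---|---|
| 30% | 62% | 90% | 8.7 points |
| 40% | 58% | 87% | 9.1 points |
| 45% | 58% | 87% | 9.1 points |
| 50% | 58% | 87% | 9.1 points |
| 55% | 59% | 88% | 8.9 points |

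**3. Is the switch reached?** It depends on the reading.

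- *Residual normality, tested.* uw-mRS takes seven values. A Shapiro-Wilk test at 0.05 on residuals with 986 patients rejected in 100% of simulated trials, for the linear and the spline model alike. Bending the NIHSS and age terms cannot make a seven-level outcome normal.
- *Central-limit argument accepted.* The linear model stands and the switch is never reached.
- *Once ordinal regression is reached.* A proportional-odds check at 0.05 on the arm term alone failed in 4-6% of simulated trials, or 12-23% if only patients without pre-stroke disability benefit. A check on all terms failed in 6-7% when the disability effect was proportional, and in every trial when only 3% of disabled patients were allowed to reach mRS 0-1. That last result largely restates its input.

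**4. Do the two ends of the chain agree?** Simulated inputs, all assumed: 592 against 394 patients; three SM mRS distributions for non-disabled patients; 30% disabled; NIHSS and age effects; arm effect set to a true 0.07 uw-mRS difference; 2,500-4,000 trials per scenario. Models adjusted for NIHSS, age and pre-stroke disability.

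| Who benefits | Linear power | Binary power | Verdicts differ |
|---|---|---|---|
| All patients | 86-94% | 74-84% | 12-19% |
| Non-disabled only | 90-96% | 90-97% | 5-10% |

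The last column compares the two models in every trial, so it is conditional on a switch to the binary model.

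**5. Type I error.** In the same simulations, the written order gave 4.7-6.2% once ordinal regression was reached. The linear model alone with robust standard errors gave 4.6-5.6%.

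**The case against.** The strongest defence is that the chain is ordered and dated, so the analyst has no free choice between models. That stands. A reader might infer inflated alpha: free choice between the linear and binary results would give about 7-9%. The SAP does not offer that choice.

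A reader might also infer that the fallback is underpowered. The documents do not show it: at the SAP's own 10-point difference, power is 87-90%. What is true is that no power is reported for it.

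Third, the verdict disagreement is not the plan's overall rate, because it presumes a switch. Under an arm-term check most switched trials would stop at ordinal regression. There, a small rerun (250 trials per set, all patients benefiting) found linear and ordinal verdicts differing in only about 6%. That stands, although a common odds shift favours the ordinal model.

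Fourth, some uw-mRS reporting survives a switch: the unadjusted means in 5.1.2, the Dawn-weight sensitivity analysis in 5.1.3 (model unspecified), and the post-hoc weighted regression. None of these requires the adjusted mean difference on the current weights.

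Finally, the simulation inputs are only partly consistent with protocol 6.A.1. They let 3% of disabled SM patients, or about 12-19% in the other set before covariates, reach mRS 0-1, where the protocol says none can. The ranges are illustrative.

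**Conclusion.** The point holds as a defect of specification. Two competent analysts could follow SAP 5.1.2 on the same data and report different primary estimands, and a reader could not tell whether either followed a rule. The final fallback also conflicts with the single primary outcome in SAP 2.2.1, the sensitivity-only role in protocol 7.B, and the rationale in protocol 6.A.1.

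Its size is conditional. If the binary model replaces the linear one, the significance verdict would differ in roughly 5-19% of trials under the assumed distributions. Site and previous TIA or stroke were not simulated, so no figure here is the exact power of the SAP model. The harm is a changed and unauditable primary estimand. Neither alpha inflation nor an underpowered fallback is established. It should be fixed, but it does not by itself invalidate the trial's result.

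SAP 5.1.1 and 5.1.2 also differ on whether covariates that are imbalanced at baseline enter the primary model. That is a separate point.

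**What to change.** **If the final data are not yet analysed.** In SAP 5.1.2, delete the clauses that promote ordinal or binary logistic regression to primary. Keep one primary analysis: linear regression of 90-day uw-mRS on group, site, baseline NIHSS, age, pre-stroke uw-mRS and previous TIA or stroke. Enter pre-stroke status once and drop the duplicate pre-morbid mRS term. Use robust standard errors and report the mean difference with its 95% CI. Keep the ordinal and mRS 0-1 models as sensitivity analyses, as protocol 7.B does. Whether the errors should also allow for clustering by week is a separate question that this change does not settle.

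**If the analysis has been run.** This looks likely, because SAP 5.1.2 describes in the past tense work added after peer review. Leave the plan unchanged. Disclose which step was reached, on what check, and whether whoever decided was blinded to arm. Report the adjusted uw-mRS mean difference with its 95% CI beside whatever was called primary.

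**Cost.** Before analysis: wording only, with no new data or patients. Intervals may be slightly wider, and a linear model is kept even if it fits imperfectly. After analysis: one further model and a short disclosure.

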5.1.3. Sensitivity Analysis of Primary Outcome

We will conduct sensitivity analyses using Dawn utility weights of the 90 day mRS. An additional sensitivity analysis will add an indicator of whether the SM subjects that were enrolled during an MSU week affect the treatment effect in a regression model by adding an indicator for these subjects. Also, in a sensitivity analysis, we will move these subjects into the MSU arm to check for consistency of results.

A further sensitivity analysis will remove subjects that were enrolled during the COVID-19 pandemic months (beginning of March, 2020).

5.1.4. Analyses of Ancillary Clinical Outcomes

We will also compare mRS at 90d (uw-mRS, Δ uw-mRS from baseline, ordinal (shift) analysis, and proportion achieving 0,1) in tPA treated patients treated within 60 minutes of LSN to patients treated 61-270 minutes, regardless of whether they were on MSU weeks vs. SM weeks. Patients on MSU weeks vs SM weeks will also be compared for differences in (a) the time from LSN to tPA treatment, (b) time from LSN, alarm time, and ED arrival to start of IAT, and for safety outcomes (i) mortality, (ii) symptomatic intracerebral hemorrhage, and (iii) incidence of tPA treated stroke mimics and transient ischemic attacks.

A logistic regression model will be used to compare 90 day mRS 0,1 vs 2-6 of patients treated with tPA within 60 minutes of symptom onset to similar patients treated 61-270 minutes after onset, adjusting for any imbalances in stroke severity (baseline NIHSS, age, premorbid mRS, and previous stroke/TIA incidence) between the groups at the time of treatment⁸. If baseline characteristics are significantly different between the two non-randomized groups, we will use propensity score analysis to limit potential bias. Also, we expect a higher incidence of spontaneous recovery (TIA) and stroke mimics may occur with earlier observation in the 0-60 minute group compared to those seen 61-270 minutes. The “natural history” of the incidence of spontaneous recovery and stroke mimics will be estimated from patients enrolled into the SM group, and will be considered in analyzing the comparison between patients treated with tPA within 0-60 min vs 61-270 min. Time to treatment and to endovascular procedures will be analyzed using Cox proportional hazards models, similarly to survival. Categorical outcomes will be analyzed using Fisher’s exact test.

Unless there is sufficient power (predetermined before the analysis is begun) the approach to ancillary analysis will generally be the calculation of confidence limits on intervention group differences rather than formal tests of significance as the trial may not have high power to detect difference in all of these outcomes. However, these comparisons will add to the knowledge of the benefits and risks of the intervention.

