1.A. Impact of stroke on individuals and populations. Stroke is the 4th leading cause of death and leading cause of serious long-term disability in the U.S. Every year, more than 795,000 people in the U.S. have a stroke with one new stroke occurring every 40 seconds¹. It is projected that by 2030 4% of the American population would have had a stroke. Stroke incidence is particularly high among younger African-Americans, lower socioeconomic groups, and in the Southeast U.S. including east Texas and Tennessee, two of the seven centers in this proposal². More than 70% of stroke patients are unable to return to their pre-stroke life style, activities of daily living and employment. AIS results from a blood clot blocking an artery to the brain and accounts for 87% of all strokes. Intravenously administered tPA is a highly effective treatment for AIS that can be carried out in the prehospital or Emergency Department (ED) setting³. Clinical trials consistently confirm the relationship of treatment success with decreased time from last-seen-normal (LSN) to initiation of treatment⁴⁻⁸. However, despite two decades of efforts to streamline Healthcare systems, most patients are treated beyond 2 hours, since treatment has been ED-based and the median door to needle times in stroke center EDs in the U.S. approximates 60 minutes^{9,10}. Such delay contributes to the overall low national tPA treatment rate--about 5% of all AIS, with only 0.0005% or 1 out of 2,000 stroke patients treated within the first hour after onset. Recently, substantially faster treatment with tPA became a reality after German researchers placed a Computed Tomography (CT) scan and physician on an ambulance with treatment safely "taken to the patient" 11. This MSU increased treatment rates from 21% to 33% with 25 min shorter time to treatment¹². Thirty-one percent of MSU tPA patients were treated within 60 minutes of onset compared to 4.9% with Standard Management (SM), and these patients had an OR of 1.93 (95% CI 1.09-3.41) of discharge to home compared to later treatment¹³. In addition, recent transformative trials 14-17 have shown substantial benefit from intra-arterial mechanical thrombectomy (IAT) for patients with the most severe strokes, and also demonstrate that patients who achieve recanalization quickly benefit most. MSUs might speed IAT by allowing prehospital identification of appropriate patients and shortening in-house delays incurred by acquiring imaging/labs, treating with tPA, and assembly of the IAT team, perhaps allowing bypass of ED evaluation altogether. Therefore, the MSU strategy may substantially improve outcomes for patients with AIS, and dramatically alter the Healthcare system for all acute stroke patients.

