- 4.C. Run-in phase. The Houston MSU went into service in May 2014. We planned a "run-in" phase to perfect our various alert mechanisms from EMS dispatch and on-scene EMTs, practice our on-scene interaction between the MSU team and the EMS squad including rendezvous, practice tPA administration and other patient management issues on board the MSU, get a preliminary evaluation of TM reliability, and rehearse our SM week interaction with EMS. The run-in phase included 9 MSU weeks and 2 SM weeks. During the MSU weeks, we were alerted 90 times, and enrolled and transported 25 patients. Reasons for non-enrollment mainly included time/wake up, hypoglycemia, syncope, TIA, seizure, migraine, and "other". During the run-in phase, we treated 13 patients with tPA on the MSU, and another patient met criteria for tPA treatment during the two SM weeks. Of the 13 tPA treated MSU patients, 31% were treated between 0-60 minutes from LSN, 38% between 61-90 minutes, 15% between 91-180 min, and 15% between 181-270 min. Of the 12 patients who were transported but not treated, the reasons for non-treatment were: 4 ICH, 3 seizures, 1 LSN >4.5 hrs, 1 SDH, 1 mimic, 2 TIA. Our average "on-scene" time for MSU transports was 28 min (range 12-53 min), with average alarm to treatment interval of 52 min (range 37-156 min). The one SM tPA eligible patient was treated in the ED during the 61-90 min interval from LSN. Of note, 4 of the 13 tPA treated patients on the MSU had baseline mRS > 2. Seven of the 12 pts with 90 day outcome data (one patient lost to f/u) had f/u mRS < 1 point higher than baseline mRS. Ten TM consultations were attempted during MSU weeks, and all were completed. There were no TM technical issues, except on one occasion, the TM signal was intermittent due to inclement weather. Agreement between the MSU VN and TM VN on whether or not to administer tPA was 89%. There were no technical issues with CT scanning or CT

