A logistic regression model will be used to compare 90 day mRS 0,1 vs 2-6 of patients treated with tPA within 60 minutes of symptom onset to similar patients treated 61-270 minutes after onset, adjusting for any imbalances in stroke severity (baseline NIHSS, age, premorbid mRS, and previous stroke/TIA incidence) between the groups at the time of treatment³⁴. If baseline characteristics are significantly different between the two non-randomized groups, we will use propensity score analysis to limit potential bias. Also, we expect a higher incidence of spontaneous recovery (TIA) and stroke mimics may occur with earlier observation in the 0-60 minute group compared to those seen 61-270 minutes. The "natural history" of the incidence of spontaneous recovery and stroke mimics will be estimated from patients enrolled into the SM group, and will be considered in analyzing the comparison between patients treated with tPA within 0-60 min vs 61-270 min. Time to treatment and to endovascular procedures will be analyzed using Cox proportional hazards models, similarly to survival. Categorical outcomes will be analyzed using Fisher's exact test.

Unless there is sufficient power (predetermined before the analysis is begun) the approach to ancillary analysis will generally be the calculation of confidence limits on intervention group differences rather than formal tests of significance as the trial may not have high power to detect difference in all of these outcomes. However, these comparisons will add to the knowledge of the benefits and risks of the intervention.

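### The comparison of tPA within 60 minutes versus 61-270 minutes is observational, yet its propensity adjustment waits on significant baseline tests, its covariates vary by section, and site is left out

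*SAP*

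**What the plan says.** SAP 2.2.2 defines the secondary comparison as "Comparing enrolled patients treated with tPA within 60 minutes of LSN onset according to published guidelines on either MSU or SM weeks" against similar patients treated at 61-270 minutes, "adjusting for any imbalances in stroke severity (baseline NIHSS) between the groups at the time of treatment". A spline analysis of time to treatment sits under the same item and lists no covariates of its own.

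SAP 5.1.4 makes the comparison "regardless of whether they were on MSU weeks vs. SM weeks". For mRS 0-1 versus 2-6 it specifies a logistic model "adjusting for any imbalances in stroke severity (baseline NIHSS, age, premorbid mRS, and previous stroke/TIA incidence) between the groups at the time of treatment". It then adds: "If baseline characteristics are significantly different between the two non-randomized groups, we will use propensity score analysis to limit potential bias". The variables of that propensity model are not given. Protocol 7.C carries the same plan.

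Site is in neither covariate list. It does appear in the primary MSU-versus-SM regression (SAP 5.1.2) and in the post hoc propensity model there. That post hoc model predicts enrolment into MSU versus EMS, not early versus late treatment.

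**The concern.** The SAP itself calls these groups non-randomized. How early a patient is treated depends on arm, site, distance, delay in calling and presentation, so control of confounding carries the whole comparison. Three features weaken it.

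- Propensity adjustment depends on a significance test. Such a test measures sample size as well as imbalance, and the early group is the small one.
- The covariates are not fixed. Section 5.1.4 names four and section 2.2.2 names one. The four are attached to the dichotomized mRS model only, and the reference to any imbalances leaves it open whether all four always enter.
- Site is missing, although SAP 5.1.5 expects demographic differences between telemedicine and on-board-neurologist sites.

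Because the arms are pooled and the MSU is meant to bring treatment forward, the early group will be mostly MSU patients. Any arm difference that does not act through time to tPA then enters the early-versus-late estimate. The protocol names candidates: faster IAT (1.A, 5.L) and a greater tendency to alert the team on MSU weeks (7.D).

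Protocol 1.B lists the added benefit of first-hour treatment as an evidence gap the study will address, and this is the analysis meant to address it.

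**Working it through.** **Inputs**

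- Share of tPA patients treated within 60 minutes: 31% MSU and 4.9% SM, from an earlier MSU study quoted in Protocol 1.A. In this trial's own run-in, "31% were treated between 0-60 minutes from LSN" among 13 MSU patients (Protocol 4.C).
- MSU:SM ratio: 1.5 in the current sample size, 1.8 originally, and described as now balanced (all SAP 4.1).
- SD 0.385, difference 0.07, 5% loss, N = 1038 (SAP 4.1). The 80% power and 0.05 alpha are stated there for the original N of 693 and are assumed to carry over.
- Balance criterion: standardized mean difference (SMD) below 0.1, used in SAP 5.1.2 for the post hoc propensity analysis.

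**Step 1. The plan's own figure.** The documents give no figure for arm mix by treatment time. The 3:2 ratio comes from the sample size, which can be checked. Total analysed = (1 + 1/1.5) × 2.5 × (0.385 × 2.80/0.07)² ≈ 989. Allowing for loss gives 989 × 1.05 ≈ 1039 or 989/0.95 ≈ 1041. The stated 1038 is reproduced.

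**Step 2. Arm mix.** Let k be the MSU:SM ratio among tPA-treated patients.

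- MSU share of early group = 0.31k / (0.31k + 0.049)
- MSU share of late group = 0.69k / (0.69k + 0.951)

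| k | Early group, MSU | Late group, MSU | Gap (points) |
|---|---|---|---|
| 1.0 | 86.4% | 42.0% | 44 |
| 1.5 | 90.5% | 52.1% | 38 |
| 1.8 | 91.9% | 56.6% | 35 |

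If the SM early rate were 10% instead of 4.9%, the MSU share of the early group would be 0.31/(0.31 + 0.10) = 76% at 1:1 and 0.465/(0.465 + 0.10) = 82% at 3:2.

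**Step 3. Size of the early group.** At 3:2 the early fraction is 0.6 × 0.31 + 0.4 × 0.049 = 0.206. With 900 treated (assumption) that is 185 early and 715 late. If all 1038 were treated it is about 213 and 825.

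**Step 4. What one baseline test can detect.** For a two-sided 5% test, power ≈ Φ(SMD / √(1/n₁ + 1/n₂) − 1.96).

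| SMD | 185 vs 715 | 213 vs 825 |
|---|---|---|
| 0.10 | 23% | 26% |
| 0.15 | 44% | 50% |
| 0.20 | 68% | 74% |

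Example: √(1/185 + 1/715) = 0.0825; 0.10/0.0825 = 1.21; Φ(1.21 − 1.96) ≈ 0.23.

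**Step 5. Consequence of the arm mix.** Write b for the arm difference in an outcome that does not act through time to tPA. The pooled contrast absorbs roughly gap × b, which is 0.38b at 3:2. The documents give no value for b.

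**The case against.** **The regression does not depend on the trigger.** A reader might infer that the comparison could stay unadjusted after a non-significant test. The text does not support that. Regression on four covariates is planned separately, and they are the four that SAP 5.1.2 itself associates with mRS. For the same reason no bias from leaving out a strong predictor can be put on this analysis: no such predictor has been identified. What stands is that the four are loosely worded, are not carried to every outcome, and exclude site.

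**The trigger looks at several characteristics.** With 185 versus 715 patients and four independent tests (assumption), one characteristic off by 0.15 SD gives a chance of 1 − 0.56 × 0.95³ = 52% that at least one test is significant. If all four are off it is 1 − 0.56⁴ = 90%. Single-test power therefore understates how often propensity analysis would be used. It still leaves the choice of analysis to chance, unrelated to whether the imbalance matters for outcome.

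**Pooling is deliberate, and arm is a cause of time to tPA.** This is fair. It argues against forcing arm into the only model. An MSU-only analysis also discards the variation in time that deployment weeks create, and what remains is driven by the patient and may be more confounded. It belongs as a sensitivity analysis.

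**The leakage has no documented size.** Also fair. Protocol 2.C names faster tPA and later IAT triage as the only evidence-based interventions that may differ between arms, Protocol 5.L plans IAT sensitivity analyses, and SAP 4.1 says the enrolment gap was mitigated. A reader might supply a value for b and quote a bias, but the documents support only that the route exists.

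**The analysis is already hedged.** SAP 3.3 asks for caution with secondary results and SAP 5.1.4 generally prefers confidence limits to tests. Neither step removes confounding.

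**Conclusion.** The point holds for one secondary, observational comparison; the primary MSU-versus-SM result is not touched. The significance trigger is a poor safeguard. One test misses an SMD of 0.1 about three times in four, so a non-significant result cannot show balance by the SAP's own criterion. That rests on 900-1038 treated patients with about 21% early.

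The arm imbalance between early and late groups is 35-44 percentage points under the quoted rates and the three ratios in the documents. The early group is 86-92% MSU, or 76-82% with a 10% SM early rate at 1:1 to 3:2. These shares are derived, not stated in the plan, and they apply enrolment ratios to tPA-treated patients. The resulting bias cannot be quantified.

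Nor do the documents show that the timing propensity model omits site or arm: its variables are simply not listed. The April 2021 change-log entry extending propensity analysis to all outcomes does not close the gap, because the model described has MSU versus EMS as its exposure.

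**What to change.** 1. Delete the significance condition in SAP 5.1.4 and the matching sentence in Protocol 7.C.
2. Fix one covariate set: site, baseline NIHSS, age, pre-stroke mRS and previous TIA/stroke. Always use it, by regression or propensity weighting, for every early-versus-late outcome and for the spline. Bring SAP 2.2.2 into line.
3. Report standardized differences between early and late groups, before and after any weighting, in place of baseline p-values.
4. Report an MSU-week-only version as a sensitivity analysis beside the pooled estimate. Leave out the few patients whom SAP 3.1 assigns to the SM arm in those weeks, so that arm is constant. State that its interval will be wider and that its remaining variation in time is patient-driven.

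The cost is SAP wording and one extra model. The listed covariates are ones the SAP already uses in its primary model, so no new data are needed.
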